### 7.1. Adverse Events and Deaths

#### 7.1.1. Adverse Event Dictionary

Clinical and laboratory adverse events (AEs) will be coded using the current version of Medical Dictionary for Regulatory Activities (MedDRA). System organ class (SOC), high-level group term (HLGT), high-level term (HLT), preferred term (PT), and lower-level term (LLT) will be provided in the AE dataset.

#### 7.1.2. Adverse Event Severity

Adverse events are graded by the investigator as Grade 1, 2, 3, 4, or 5 according to toxicity criteria specified in the protocol. The severity grade of events for which the investigator did not record severity will be categorized as “missing” for tabular summaries and data listings. The missing category will be listed last in the summary presentation.

#### 7.1.3. Relationship of Adverse Events to Study Drug

Related AEs are those for which the investigator selected “Related” on the AE eCRF to the question of “Related to Study Treatment.” Relatedness will always reflect the investigator assessment of causality rather than the Sponsor’s. Events for which the investigator did not record relationship to study drug will be considered related to study drug for summary purposes. However, by-subject data listings will show the relationship as missing.

#### 7.1.4. Serious Adverse Events

Serious adverse events (SAEs) will be identified and captured as SAEs if AEs met the definitions of SAE specified in the study protocol. SAEs captured and stored in the clinical database will be reconciled with the SAEs captured in the Gilead safety database before data finalization.

#### 7.1.5. Treatment-Emergent Adverse Events

##### 7.1.5.1. Definition of Treatment-Emergent Adverse Events

Treatment-emergent adverse events (TEAEs) are defined as 1 or both of the following:

- Any AEs with an onset date on or after the study drug start date (Day 1) and no later than 30 days after permanent discontinuation of study drug
- Any AEs leading to premature discontinuation of study drug.

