3.6. Luminal Disease Activity - Non-Response Criteria

Subjects who are non-responders to study treatment for luminal disease activity are subjects who either:

- Had a baseline CDAI ≥ 220 and never achieve a ≥ 70 -point CDAI reduction from baseline at any point up to and including Week 10 OR
- Had a baseline CDAI score < 220 and have an increase in CDAI of ≥ 100 points from baseline, with CDAI ≥ 220 at Week 10

These subjects will be offered the option to receive open-label filgotinib by entering into the separate LTE study. Subjects will remain blinded to their treatment allocation in the current study. Subjects meeting non-response criteria should undergo a pelvic MRI and flexible sigmoidoscopy prior to exiting the study (Refer to Sections 6.5 and 6.6 for details regarding the flexible sigmoidoscopy and MRI).

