3.8. Luminal Disease Activity - Disease Worsening Criteria

Subjects meeting the following disease worsening criterion after Week 10 must be discontinued from blinded treatment and will be offered the option to receive open-label filgotinib by entering into the separate LTE study:

- An increase in CDAI of ≥ 100 points from the Week 10 value with CDAI ≥ 220 at 2 consecutive visits

Determination of disease worsening may be made at scheduled or unscheduled visits (eg, a study visit followed by an unscheduled visit, or 2 sequential unscheduled visits anytime subsequent to the Week 10 visit).

- All subjects meeting disease worsening criteria should undergo a pelvic MRI and flexible sigmoidoscopy prior to exiting the study (Refer to Sections 6.5 and 6.6 for details regarding the flexible sigmoidoscopy and MRI).
- If a subject experiences significant worsening of underlying CD, which requires any of the prohibited medications (refer to Section 5.4.2), or surgical intervention at any point during the study, treatment discontinuation should be considered at investigator's discretion, in consultation with medical monitor if feasible (refer to Section 3.5.2); these subjects do not qualify for LTE study.

[figure not shown]

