7.3.1. Adverse Events

Following initiation of study drug, all AEs, regardless of cause or relationship, until 30-days after last administration of study IMP must be reported to the eCRF database as instructed.

All AEs should be followed up until resolution or until the AE is stable, if possible. Gilead may request that certain AEs be followed beyond the protocol defined follow up period.

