8.6.2. Adverse Events

Adverse events will be coded using the Medical Dictionary for Regulatory Activities (MedDRA). System Organ Class (SOC), High-Level Group Term (HLGT), High-Level Term (HLT), Preferred Term (PT), and Lower-Level Term (LLT) will be attached to the clinical database.

Treatment-Emergent Adverse Events (TEAEs) are defined as 1 or both of the following:

- Any AEs with an onset date of on or after the study drug start date for the entire study (Day 1) and up to 30 days after permanent discontinuation of study drug.
- Any AEs leading to premature discontinuation of study drug.

Summaries (number and percentage of subjects) of TEAEs by SOC and PT will be provided by treatment group. TEAEs will also be summarized by relationship to study drug and severity. In addition, TEAEs leading to premature discontinuation of study drug will be summarized and listed.

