### **3.7. Analysis Visit Windows**

#### **3.7.1. Definitions**

The First Dosing Date is defined as the date when subjects take the first dose of study drug, as recorded in the Study Drug Administration eCRF.

The Last Dosing Date is defined as the date when subjects take the last dose of study drug as recorded in the Study Drug Administration eCRF.

Study Day will be calculated from the first dosing date of study drug and derived as follows:

- For days on or after first dosing date: Assessment Date – First Dosing Date + 1
- For days prior to the first dosing date: Assessment Date – First Dosing Date

Therefore, Study Day 1 is the day of the first dose of study drug administration.

Baseline is defined as the last available observation prior to or on the first dosing date, unless specified otherwise.

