## 7. SAFETY ANALYSES

Unless otherwise specified, summaries of safety data will be provided for the Safety Analysis Set and will include data collected up to the last dose of study drug plus 30 days.

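### The 30-day adverse-event window has no cut at the first extension-study dose, so events that start on open-label filgotinib would be tabulated under the original arm, placebo included

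*SAP*

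**What the plan says.** **Window.** SAP 7.1.5.1 closes the treatment-emergent period "no later than 30 days after permanent discontinuation of study drug". Protocol 8.6.2 has the same limit, "up to 30 days after permanent discontinuation of study drug". SAP 7 applies it to the safety summaries generally, which "will include data collected up to the last dose of study drug plus 30 days". The anchor is this study's own dosing record, as SAP 3.7.1 makes plain: "The Last Dosing Date is defined as the date when subjects take the last dose of study drug as recorded in the Study Drug Administration". Dosing in the extension study neither moves nor closes the window.

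**Collection.** Protocol 7.3.1 requires that, once study drug has started, "all AEs, regardless of cause or relationship, until 30-days after last administration of study IMP must be reported to the eCRF database as instructed". It makes no exception for extension entrants.

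**Open-label drug.** On luminal non-responders at Week 10, Protocol 3.6 says "These subjects will be offered the option to receive open-label filgotinib by entering into the separate LTE study". Protocol 3.7 makes the same offer to perianal non-responders. Protocol 3.8 covers the period after Week 10 and says that subjects whose disease worsens "must be discontinued from blinded treatment and will be offered the option to receive open-label filgotinib by entering into the separate LTE study". Protocol 3.2 and 6.13 let extension entrants skip the post-treatment visit, which otherwise falls 30 days after the last dose.

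**Arm.** SAP 3.2 groups the Safety Analysis Set by treatment actually received, but lets this differ from the randomised arm only if the difference lasted throughout treatment.

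**The concern.** Each rule is ordinary on its own, but together they misattribute events. A placebo subject who leaves at Week 10 and starts open-label filgotinib at once is on active drug for most or all of the 30-day tail, yet still counts as placebo. A subject from a filgotinib arm may move to a different dose: for subjects with disease worsening, Protocol 5.3 names 200 mg open-label, or 100 mg for US males who are not dual refractory. Events in that tail would be shown under the dose the subject has left.

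Safety and tolerability is a stated objective. The safety tables are descriptive, with no tests, so the raw percentages by arm are the evidence, and the placebo denominator is only 15. A few events on active drug counted under placebo would blur the comparison the tables exist to show. No visible section of either document cuts the window at the first extension dose or flags events that start after it. SAP 7.7 declares no departure from the protocol's safety analyses.

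**Working it through.** **Inputs**
- Arm sizes: 75 × 2/5 = 30, 75 × 2/5 = 30, 75 × 1/5 = 15. This reproduces the 30/30/15 in SAP 1.3 and Protocol 8.8.
- Visit days (Protocol Appendix 2): Week 10 = Day 71, Week 14 = Day 99, Week 18 = Day 127.
- Tail after the last dose: 30 days.
- Not given: the number of exits to open-label drug, their split by arm, the gap before the first extension dose, and the event rate on open-label drug.

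**Step 1: can open-label dosing fall inside the window?** Yes. The post-treatment visit is due 30 days after the last dose, and extension entrants go in without it. That implies entry before Day 30 of the tail.

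**Step 2: which arm holds the event?** A subject who took placebo throughout this study did not receive a different treatment for the whole treatment period. SAP 3.2 therefore leaves the subject in placebo.

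**Step 3: how much of the window is affected?** Assume the last dose is on the exit day and extension dosing starts the next day. The share is 30 / (exit day + 30):
- Exit on Day 71: 30/101 = 29.7%, or about 30 of 100 days.
- Exit on Day 99: 30/129 = 23.3%.
- Exit on Day 127: 30/157 = 19.1%.

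Any gap before the first extension dose lowers these figures, so they are upper limits. With the window cut at the first extension dose, a Week 10 exit has 71 days in place of 101.

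**Step 4: what does one subject do to a table?** SAP 7.1.6.1 counts each subject once per summary, so only a first event in a category matters.
- Placebo: 1/15 = 6.7 points.
- Filgotinib arm: 1/30 = 3.3 points.

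**Step 5: illustration, all inputs assumed.** Let *e* placebo subjects move to open-label drug, each with probability *q* of a first event in the category during the tail. The mean shift is 100 × *e* × *q* / 15 points, and the chance of at least one misattributed subject is 1 − (1 − *q*)^*e*.
- *e* = 3, *q* = 0.10: shift 2.0 points; chance 1 − 0.9³ = 27%.
- *e* = 5, *q* = 0.20: shift 6.7 points; chance 1 − 0.8⁵ = 67%.
- Over *e* = 2 to 8 and *q* = 0.05 to 0.30: mean shift from 100 × 2 × 0.05 / 15 = 0.7 points to 100 × 8 × 0.30 / 15 = 16 points.

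The width of that range shows how little the documents fix. It is not a forecast.

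**Step 6: partial dates.** SAP 7.1.5.2 compares an incomplete onset date, by month or year, with the date 30 days after the last dose. An event with an incomplete date that began after extension entry can therefore also default to treatment-emergent.

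**The case against.** The strongest reply is that the events may never reach this database. Protocol 7.3.1 says "until 30-days after last administration of study IMP must be reported to the eCRF database as instructed". It does not mention the extension study, and the instructions it points to are not in the documents. Protocol 6.13 waives the post-treatment assessments for extension entrants, and the waived list includes the adverse-event review and the blood samples. This stands as a limit: reporting is required, but the visit that would secure it is removed. It does not clear the plan. If such events go only to the extension database, roll-over subjects have shorter follow-up here than those who opt out, and no rule covers that either.

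A reader might infer four stronger points that the documents do not support:
- *That laboratory changes on open-label drug are counted under placebo.* Protocol 7.3.1 concerns adverse events only, and no scheduled sample in this study after extension entry is shown.
- *That a share of placebo person-time measures the error.* The adverse-event tables count subjects, not person-time, and a subject with an earlier event in the same category is already counted.
- *That placebo subjects leave most often, so the error has a known direction.* No exit figures are given. A misattributed placebo event can only raise the placebo percentage, but the filgotinib arms can gain tail events too, so the net effect on the contrast is not determined.
- *That every roll-over from a filgotinib arm changes dose.* Protocol 5.3 shows this depends on the subject.

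It is also fair that the SAP and protocol definitions agree and that individual adverse events are listed. Agreement does not correct the attribution, and the planned listings flag treatment-emergence by the same rule.

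**Conclusion.** The point holds as a rule that, followed as written, attributes adverse events on open-label filgotinib to the arm the subject has left. It affects only Week 10 non-responders and worsening subjects who are eligible for the extension, accept it, and start dosing within 30 days. Week 24 completers are outside the point: they continue study drug blinded.

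The size is up to about 30 of 100 window days for an immediate Week 10 roll-over, and 6.7 points on a placebo percentage for each placebo subject whose first event in a category falls there. The total effect cannot be computed, because exits, their balance across arms, the gap before dosing and completeness of capture are not stated. The SAP should be changed, because each possible handling of these events leaves a difference between subjects that no rule addresses.

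**What to change.** In SAP 7 and 7.1.5.1, state that for subjects who enter the extension on open-label filgotinib the adverse-event window ends at the earlier of last dose plus 30 days and the day before the first extension-study dose. List later-onset events separately. Carry the same limit into the partial-date rule in SAP 7.1.5.2, and apply it to any laboratory record dated after that dose. State which database holds adverse events that start after extension entry.

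This needs a short addition to the SAP and one date from the extension study. It changes no visit, treatment or clinical procedure. The downside is slightly shorter adverse-event follow-up for roll-over subjects than for those who opt out, so late-onset events from blinded treatment in roll-over subjects would appear only in the separate listing. The report should say so beside the tables.

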#### 7.1.5.2. Incomplete Dates

If the onset date of the AE is incomplete and the AE stop date is not prior to the first dosing date of study drug, then the month and year (or year alone if month is not recorded) of onset determine whether an AE is treatment emergent. The event is considered treatment emergent if both of the following 2 criteria are met:

- The AE onset date is the same as or after the month and year (or year) of the first dosing date of study drug, and
- The AE onset date is the same as or before the month and year (or year) of the date corresponding to 30 days after the date of the last dose of study drug

An AE with completely missing onset and stop dates, or with the onset date missing and a stop date later than the first dosing date of study drug, will be considered to be treatment emergent. In addition, an AE with the onset date missing and an incomplete stop date with the same or later month and year (or year alone if month is not recorded) as the first dosing date of study drug will be considered treatment emergent.

#### 7.1.6. Summaries of Adverse Events and Deaths

Treatment-emergent AEs will be summarized based on the Safety Analysis Set. No formal statistical testing is planned.

##### 7.1.6.1. Summaries of AE Incidence

The number and percentage of subjects who reported at least 1 TEAE will be provided and summarized by SOC, HLT, PT, and treatment group. For other AEs described below, summaries will be provided by SOC, PT, and treatment group:

- TEAEs of Grade 3 or higher (by maximum severity)
- TEAEs of Grade 2 or higher (by maximum severity)
- All TE treatment-related AEs
- TE treatment-related AEs of Grade 3 or higher (by maximum severity)
- TE treatment-related AEs of Grade 2 or higher (by maximum severity)
- All TE SAEs
- All TE treatment-related SAEs
- All TEAEs leading to premature discontinuation of study drug

- All TEAEs leading to premature discontinuation of study
- All TE SAEs leading to death (ie, outcome of death)
- All TEAEs leading to temporary interruption of study drug

A brief, high-level summary of AEs described above will be provided by treatment group presenting the number and percentage of subjects who reported the above AEs. All deaths observed in the study will be also included in this summary.

Multiple events will be counted only once per subject in each summary. Adverse events will be summarized and listed first in alphabetic order of SOC and HLT within each SOC (if applicable), and then by PT in descending order of total frequency within each SOC. For summaries by severity grade, the most severe grade will be used for those AEs that occurred more than once in an individual subject during the study.

In addition, the following tables will be generated and summarized by PT only, in descending order of total frequency:

- TEAEs
- TEAEs of Grade 3 or higher
- TEAEs of Grade 2 or higher
- TE SAEs
- TE treatment-related AEs
- TE treatment-related SAEs
- TEAEs leading to premature discontinuation of study drug

Data listings will be provided for the following:

- All AEs, indicating whether the event is treatment emergent
- All AEs of Grade 3 or higher
- All AEs of Grade 2 or higher
- SAEs
- Deaths
- All AEs leading to death (ie, outcome of death)

- AEs leading to premature discontinuation of study drug
- AEs leading to premature discontinuation of study
- AEs leading to temporary interruption of study drug

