3.4. Duration of Treatment

Randomized subjects will receive a maximum of 24 weeks of study drug. Subjects who are non-responders based on the results of the Week 10 assessments (see Section 3.6 OR Section 3.7 or meeting disease worsening criteria after Week 10 (see Section 3.8) must be discontinued from blinded treatment (see Section 3.5.2).

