### **4.2.1. Duration of Exposure to Study Drug**

Total duration of exposure to study drug will be defined as last dosing date minus first dosing date plus 1, regardless of any temporary interruptions in study drug administration, and will be expressed in weeks using up to 1 decimal place (eg, 4.5 weeks). If the last study drug dosing date is missing, the latest date among the study drug end date, clinical visit date, laboratory sample collection date, and vital signs assessment date that occurred during the on-treatment period will be used.

The total duration of exposure to study drug will be summarized using descriptive statistics (n, mean, SD, median, Q1, Q3, minimum, and maximum) and using the number (ie, cumulative counts) and percentage of subjects exposed through the following time periods: 1 day, 2 weeks, 4 weeks, 6 weeks, 10 weeks, 14 weeks, 18 weeks, 20 weeks and 24 weeks. Summaries will be provided by treatment group for the Safety Analysis Set.

No formal statistical testing is planned.

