### 7.1.7. Adverse Events of Interest

Adverse events of interest (AEI) include infections, malignancies (excluding nonmelanoma skin cancers), nonmelanoma skin cancers, gastrointestinal perforations, major adverse cardiovascular events (MACE), and thromboembolic events. Summaries of the following treatment-emergent AEIs will be produced to enhance the analysis of safety data.

- Events of infections, presented in the following subcategories:
  - AEs of infections, utilizing all AEs in the MedDRA Infections and Infestations SOC
  - AEs of serious infections, using all AEs in the MedDRA Infections and Infestations SOC that are classified as SAEs
  - AEs of herpes zoster, utilizing a MedDRA search term (MST) list developed by Gilead
  - AEs of opportunistic infections (OIs), utilizing a narrow scope Standardised MedDRA Query (SMQ)
- AEs of malignancies, excluding nonmelanoma skin cancers, utilizing an MST list developed by Gilead
- AEs of nonmelanoma skin cancers, utilizing an MST list developed by Gilead
- AEs of gastrointestinal perforations, utilizing an MST list developed by Gilead
- AEs of MACE, utilizing a positively adjudicated event list, presented in the following subcategories (Section 7.1.7.1):
  - Cardiovascular (CV) death
  - Non-fatal myocardial infarction (MI)
  - Non-fatal stroke
- AEs of arterial systemic thromboembolism (ASTE), utilizing a positively adjudicated event list (Section 7.1.7.1)
- AEs of venous thromboembolism (VTE), utilizing a positively adjudicated event list (Section 7.1.7.1)

The number and percentage of subjects with a reported event will be summarized for each treatment group by PT for each AEI category. Data listings for AEIs will also be provided.

The number and percentage of subjects with positively adjudicated TE MACE, TE ASTE and TE VTE will be summarized by treatment group using the adjudicated category, if applicable.

A by-subject listing of subjects with potential events for adjudication (MACE, ASTE, and VTE) and their respective adjudication results will be provided.

A by-subject listing of thromboembolic history and risk factors will be provided for subjects with potential events for adjudication (MACE, ASTE, and VTE).

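### Adverse-event tables use crude percentages although CDAI or PDAI failure from Week 10 ends treatment; add a Week 10 summary and, for common categories only, exposure-adjusted rates

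*SAP*

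**What the plan says.** **How events are counted.** Protocol 8.6.2 states: "Summaries (number and percentage of subjects) of TEAEs by SOC and PT will be provided by treatment group". SAP 7.1.6.1 repeats this with an added MedDRA level: "The number and percentage of subjects who reported at least 1 TEAE will be provided and summarized by SOC, HLT, PT, and treatment group". It also says: "Multiple events will be counted only once per subject in each summary". For adverse events of interest, SAP 7.1.7 states: "The number and percentage of subjects with a reported event will be summarized for each treatment group by PT for each AEI category". SAP 7 and 7.1.5.1 close the counting window 30 days after each subject's own last dose.

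**How long subjects are observed.** Protocol 3.4 sets the ceiling: "Randomized subjects will receive a maximum of 24 weeks of study drug". It also says that Week 10 non-responders and later worseners "must be discontinued from blinded treatment". Protocol 3.8 repeats the rule for worsening: "Subjects meeting the following disease worsening criterion after Week 10 must be discontinued from blinded treatment". The criteria are in Protocol 3.6 (luminal, CDAI), 3.7 (perianal symptoms, PDAI subscores) and 3.8 (CDAI worsening). Subjects who enter the extension study skip the post-treatment safety visit (Protocol 3.2, SAP 1.2).

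**What is done about exposure.** SAP 4.2.1 states: "Total duration of exposure to study drug will be defined as last dosing date minus first dosing date plus 1". It tabulates this duration by arm, with cumulative counts at set time points. The visible adverse-event sections contain no person-time denominator, no time-to-first-event analysis and no summary restricted to the first 10 weeks.

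**The concern.** Time under observation depends on how well treatment works. A subject who leaves at Week 10 has less time in which to have a first event than one who stays to Week 24, yet each counts as one subject in the denominator. If one arm loses more subjects to these rules, its crude percentage falls even when its event rate per week on study is the same. The exposure table would show the imbalance but would not correct the percentages.

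Safety and tolerability is a stated secondary objective. No testing is planned for adverse events, so the percentages shown side by side are the whole comparison. Protocol 1.5 already reports more infections on active treatment than on placebo across filgotinib studies, so an exposure artefact could affect the category that readers will examine most closely.

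**Working it through.** **The plan's own figures.** The plan states no adverse-event rate and no expected exit share. Its only numerical table is the set of exact 90% intervals for response with n = 30 (Protocol Table 8-1, SAP Table 1-1). All 14 limits reproduce by the Clopper-Pearson method (for example 15/30 gives 33.9% to 66.1%, printed as 34% and 66%). Nothing in that table is disputed.

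**Inputs from the documents.** Week 10 exit; 24-week maximum; 30-day window (30/7 = 4.3 weeks); arm sizes 30, 30 and 15.

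**Assumptions.** The hazard of a first event is constant and the same in both arms. The risk over 24 weeks is 60%. All efficacy exits occur at Week 10, with share x. The values of x are assumed.

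**Formulas.** Hazard λ = −ln(0.4)/24 = 0.03818 per week. Risk by t weeks is R(t) = 1 − exp(−λt). Crude percentage = x·R(t1) + (1 − x)·R(t2). Hence the gap between arms = (difference in x) × [R(t2) − R(t1)].

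- No follow-up after the last dose: R(10) = 31.7%, R(24) = 60.0%, difference 28.3 points.
- Full 30-day window for all: R(14.3) = 42.0%, R(28.3) = 66.0%, difference 24.0 points.

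| Exit share, arm A / arm B | Crude %, no tail (A / B) | Gap | Crude %, 30-day tail (A / B) | Gap |
|---|---|---|---|---|
| 25% / 15% | 52.9 / 55.8 | 2.8 | 60.0 / 62.4 | 2.4 |
| 40% / 25% | 48.7 / 52.9 | 4.2 | 56.4 / 60.0 | 3.6 |
| 50% / 30% | 45.9 / 51.5 | 5.7 | 54.0 / 58.8 | 4.8 |

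Gaps are taken before rounding. Equal exit shares give a gap of zero. Because extension entrants skip the post-treatment visit, the true position may lie between the two halves of the table.

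**Against one subject.** One placebo subject is 1/15 = 6.7 points. To reach that, exit shares would have to differ by 6.67/28.3 = 24 percentage points without the tail, or 6.67/24.0 = 28 with it.

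**A rough scale from the protocol.** Protocol 1.4 cites 59% versus 41% response in the sponsor's earlier Phase 2 Crohn's disease trial, so 41% versus 59% non-response. Applying those shares to everyone, with a 50% risk over 24 weeks and no tail, gives 39.8% versus 35.3%. If only half the subjects have baseline CDAI ≥220, it gives 44.9% versus 42.6%. That trial defined response as a 100-point CDAI fall (Protocol 1.2.3.1), whereas Protocol 3.6 uses a 70-point fall, so this is a scale and not a forecast.

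**What a person-time rate does.** Under a constant hazard, expected time at risk to first event over t weeks is R(t)/λ. Subjects with an event divided by time at risk is therefore λ, whatever the mix of leavers and stayers: 0.03818 × 52 = 1.99 per person-year in both arms, in every row.

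**Why not for rare events.** In the third row mean treatment time is 0.5×10 + 0.5×24 = 17.0 weeks and 0.3×10 + 0.7×24 = 19.8 weeks. Fifteen placebo subjects then contribute 15×17.0/52 = 4.9 to 15×19.8/52 = 5.7 person-years. One event would read as about 18 to 20 per 100 person-years. One event among 30 subjects at 19.8 weeks (11.4 person-years) would read as about 9.

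**The case against.** The strongest reply is that the effect is small beside the noise. At about 50% versus 55% with 15 and 30 subjects, the standard error of the difference is √(0.25/15 + 0.2475/30) = 16 points, a 90% half-width of about 26. The study is declared descriptive, and the imbalance can be seen from the exposure table, the discontinuation reasons and the by-subject listings. All of that stands, and it makes this a reporting refinement, not an error in the plan.

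Two stronger readings are tempting. A reader might infer that every subject without fistula response leaves at Week 10. The documents do not say so. Exit needs baseline CDAI ≥220 without a 70-point fall, or baseline CDAI <220 with a rise of at least 100 points to ≥220, or a raised and worsened PDAI discharge or pain subscore at both Week 6 and Week 10. A reader might also infer that the tables will overstate filgotinib's risk. That follows only if placebo loses more subjects; no baseline CDAI mix or exit share is given, and the direction would reverse if an active arm lost more.

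Constant hazard is also open to challenge. Leavers have more active disease, and Protocol 7.1.1 allows complications from lack of efficacy to count as adverse events. Exposure adjustment does not correct for that. This limits the person-time rates; it does not affect a summary cut at Week 10.

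**Conclusion.** The point holds as a minor analysis weakness. Exit driven by CDAI and PDAI outcomes, combined with crude percentages over a window tied to each subject's own last dose, can produce a difference between arms when event hazards are equal. Under the assumed exits and a 60% risk the false gap is 2.4 to 4.8 points with the full window and 2.8 to 5.7 without it, always towards the arm that stays longer. The size rests on assumed exit shares, a constant and equal hazard, and all exits falling at Week 10. The documents support the mechanism, but not a particular size and not a claim that filgotinib will be the arm disadvantaged.

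**What to change.** Keep the crude tables and add to SAP 7.1.6.1 and 7.1.7:

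- **(a) Events up to Week 10.** Number and percentage of subjects with any TEAE, any SAE, any infection and any serious infection with onset from first dose up to Day 71, before the mandatory efficacy exits. Include a simple rule for partial onset dates, because SAP 7.1.5.2 only decides whether such events are treatment-emergent.
- **(b) Exposure-adjusted incidence.** For any TEAE, SAEs and infections only: first-event incidence by arm with a 90% CI. Time at risk runs to the first event or to the end of the last-dose-plus-30-days window, or to extension-study entry if earlier.
- **(c) Rare events of interest.** Report MACE, VTE, malignancy and perforation as counts with person-years shown, not as rates.

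The cost is a few extra tables, one partial-date rule and one new time-at-risk variable, since SAP 4.2.1 derives only first-to-last-dose duration. The dates needed are already collected. Summary (a) needs no hazard assumption but leaves out later events and does not address early withdrawal for other reasons. Summary (b) covers the whole period but assumes a roughly constant hazard and does not correct for leavers having a different hazard from stayers. Trial conduct does not change.
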